8.3.1. General Information on Immune-Related Adverse Events

The immune-modulating properties of checkpoint-inhibitors, such as the anti-PD-L1 antibody atezolizumab, are able to unbalance immunologic tolerance and generate a subset of AEs (called irAEs) with an autoimmune inflammatory pathomechanism. Immune-related adverse events may involve any organ or tissue (Michot et al 2016). Most irAEs occur within the first 12 weeks of exposure to ICIs but some of them may appear with a delayed onset. Diagnosis of irAEs should be based on exposure to an ICI and a reasonable immune-based mechanism of the observed AE. Whenever possible, histologic examination or other immune-based diagnostic evaluations should be used to support the diagnosis. Other etiologic causes including AEs from tumor progression should be ruled out.

The spectrum of irAEs is wide and can be general or organ-specific. Examples of general irAEs in subjects treated with ICIs are fatigue, fever, and chills. Organ-specific irAEs consist of dermatitis (rash, pruritus, vitiligo, oral mucositis, and gingivitis), enterocolitis (diarrhea with abdominal pain and clinical or radiological evidence of colonic inflammation), and endocrinopathies (pituitary, thyroid, adrenal, testes). Diagnosis of endocrine dysfunction is challenging with relatively unspecific symptoms. Additional laboratory testing of the endocrine axes may be helpful: prolactin (pituitary-hypothalamic function), FT4 and TSH (pituitary-thyroid function), luteinizing hormone (LH) and FSH (pituitary-gonadal function), adrenocorticotrophic hormone (ACTH) and cortisol (pituitary-adrenal function).

Additional organ-specific irAEs include hepatitis (AST/ALT increases, hepatomegaly, periportal edema, periportal lymphadenopathy, lymphocyte infiltrates periportal and surrounding primary biliary ducts) and pneumonitis (acute interstitial pneumonia). Less frequent irAEs include neurologic disorders (myasthenia gravis, Guillain-Barré syndrome, aseptic meningitis, myelitis, facial paresis), ocular AEs (uveitis), renal AEs (interstitial nephritis), cardiac AEs (myocarditis), muscular AEs (myositis), skin-related AEs (Stevens-Johnson syndrome, toxic epidermal necrolysis), and pancreatic AEs (lipase increase).

8.4. Follow-Up of Adverse Events

Non-serious AEs (see below for AESIs [[Table 31](#)]) are to be recorded in the CRF until 30 days after the date of the decision to discontinue study treatment (the later of the date of the decision

by the investigator to permanently discontinue study treatment or the date of the last dose of any study treatment taken by the subject). The status of unrelated SAEs that are ongoing after the date of the decision to discontinue study treatment will be documented as of the 100-day FU-2 visit.

All AESIs (regardless of seriousness) and all related SAEs that are ongoing 100 days after the date of the decision to discontinue study treatment (the later of the date of the decision by the investigator to permanently discontinue study treatment or the date of the last dose of any study treatment taken by the subject), and AEs assessed as related that led to study treatment discontinuation that are ongoing 100 days after the date of the decision to discontinue study treatment, are to be followed until either:

- the AE has resolved
- the AE has improved to Grade 2 or lower
- The Investigator determines that the event has become stable or irreversible.

Further details on follow-up procedures are summarized in [Appendix K](#).

8.5. Other Safety Considerations

8.5.1. Pregnancy

Use of highly effective methods of contraception is very important during the study and for 5 months after the last dose of study treatment. If a subject becomes pregnant during the study, she will be taken off study treatment. She will be followed through the end of her pregnancy and the infant should have follow up for at least 6 months after birth. Furthermore, male subjects must refrain from donating sperm and are required to use condoms in order to avoid transmission of study treatment in semen for the duration of study treatment and through 5 months after their last dose of study treatment. If a female partner of a male subject becomes pregnant during the study, the Sponsor will ask the pregnant female partner to be followed through the end of her pregnancy and for the infant to be followed for at least 6 months after birth. Both male and female subjects should seek advice and consider fertility preservation before receiving study treatment.

The Investigator must inform the Sponsor of the pregnancy. Forms for reporting pregnancies will be provided to the study sites upon request. The outcome of a pregnancy (for a subject or for the partner of a subject) and the medical condition of any resultant offspring must be reported to the Sponsor or designee. Any birth defect or congenital anomaly must be reported as an SAE and

any other untoward events occurring during the pregnancy must be reported as AEs or SAEs, as appropriate.

Females should not breastfeed while receiving study treatment and for the following periods after discontinuing study treatment:

- **Cabozantinib + atezolizumab:** at least 5 months from the last dose of atezolizumab or 4 months from the last dose of cabozantinib, whichever is later
- **Sorafenib:** at least 2 weeks after the last dose of sorafenib
- **Single-agent cabozantinib:** at least 4 months from the last dose of cabozantinib

8.5.2. Medication Errors/Overdose

Medication error is defined as the administration of study drug medication outside or above the established dosing regimens per the specific protocol.

Any study medication overdose, misuse, abuse, or study medication error (excluding missed doses) that results in an AE or SAE requires reporting to the Sponsor or designee according to the guidance for AE and SAE reporting ([Sections 8.1](#) and [8.2](#), respectively).

In case of overdose, the Sponsor medical monitor or designee should be contacted promptly to discuss how to proceed. Any AEs that occur as a result of an overdose have to be treated according to clinical standard practice.

Please refer to the Investigator's Brochure for additional management recommendations for an overdose of cabozantinib.

9. STATISTICAL CONSIDERATIONS

Details of the planned analyses, including sensitivity analyses or other strategies if needed to assess and address consequences of the COVID-19 pandemic on trial conduct and study data, will be provided in a separate Statistical Analysis Plan (SAP) that will be finalized before the last subject is randomized. The statistical principles applied in the design and planned analyses of this study are consistent with ICH E9 and FDA Guidance for Industry: Clinical Trial Endpoints for the Approval of Cancer Drugs and Biologics (2018).

9.1. Analysis Populations

The planned analysis populations to be employed for statistical analyses of data collected from subjects randomized during the global enrollment phase are briefly summarized in [Table 32](#). These populations will include subjects in China randomized during the global enrollment phase. Subjects randomized during the Mainland China Extension Phase are excluded from these analyses; they will be included in separate analyses ([see Section 9.9](#)). Further information on these populations is provided in the sections below.

Table 32: Analysis Populations for the Global Enrollment Phase

Analysis	Population	Subjects
Primary PFS	PITT	First 372 subjects randomized to experimental or control arm (may be expanded to include the first 410 randomized subjects)
Primary OS	ITT	ITT subjects randomized to experimental or control arm
Secondary PFS	ITT	ITT subjects in control and single-agent cabozantinib arm
Additional efficacy analyses	ITT	All randomized subjects
Safety analyses	Safety	All subjects who received any study treatment

ITT, Intent-to-Treat; OS, overall survival; PFS, progression-free survival; PITT, PFS Intent-to-Treat.

9.1.1. Intention-to-Treat Population

The ITT population will consist of all subjects who are randomized to any of the three study treatment arms (the experimental arm [cabozantinib plus atezolizumab], the single-agent

cabozantinib arm, or the control arm [sorafenib]) during the global enrollment phase, regardless of whether any study treatment or the correct study treatment is received. This population will be used for the primary OS analysis to compare the combination arm with the control arm (sorafenib), and also for the secondary PFS analysis to compare the single-agent cabozantinib arm with the control arm (sorafenib). Subjects randomized during the Mainland China Extension Phase are excluded from this population; they will be included in separate analyses ([see Section 9.9](#)).

9.1.1.1. PFS Intention-to-Treat Population

The first 372 subjects that are randomized (based upon Greenwich Mean Time randomization date/time values) to the experimental (cabozantinib and atezolizumab, n=248) arm and control (sorafenib, n=124) arm will be considered as the PFS Intent-to Treat (PITT) population. The population may be extended to the first 410 subjects randomized to the two groups if a review of accumulating events suggests that the number of events required will not be reached (due to censoring) among the first 372 subjects originally planned. This population will be used for the primary PFS analysis to compare these arms.

9.1.2. Safety Population

The Safety population will consist of all subjects who randomized during the global enrollment phase and receive any amount of study treatment. Analyses based on Safety population will be performed according to the actual treatment received for the length of the study. Data handling rules for subjects in the experimental/control arm who received incorrect study treatment will be described in the SAP. Subjects randomized during the Mainland China Extension Phase are excluded from this population; they will be included in separate analyses ([see Section 9.9](#)).

9.2. Primary Efficacy Endpoints

The two primary efficacy endpoints are duration of PFS and OS. Subjects randomized to the experimental (cabozantinib and atezolizumab) arm and control (sorafenib) arm during the global enrollment phase will be considered for these analyses. Subjects randomized during the Mainland China Extension Phase will not be included in these analyses; they will be included in separate analyses ([see Section 9.9](#)).

9.2.1. Definitions

9.2.1.1. Duration of Progression-Free Survival

Duration of PFS is defined as the time from randomization to the earlier of either radiographic PD per RECIST 1.1 or death due to any cause. The definition of disease progression and censoring rules for the primary analysis are described in [Section 9.2.2](#).

9.2.1.2. Duration of Overall Survival

Duration of OS is defined as the time from date of randomization to date of death due to any cause. For subjects who are alive at the time of data cutoff or are permanently lost to follow-up, duration of OS will be right censored at the earlier of the following: date the subject withdrew consent from all follow-up, data cutoff date, or the date the subject was last known to be alive.

9.2.2. Primary Analysis

9.2.2.1. Progression-Free Survival

The primary analysis of PFS is event-driven and will be conducted after at least 257 events have been observed in the PITT population (see [Section 9.1.1.1](#)). It is designed to include progression events as determined by the BIRC per RECIST 1.1. Clinical deterioration determined by the investigator will not be considered progression events.

General censoring rules for the primary analysis of PFS are described below:

- Subjects who receive systemic NPACT or nonprotocol radiation therapy (other than to bone) or surgery to resect target lesions before experiencing an event will be right censored at the date of the last tumor assessment prior to the date of initiation of subsequent therapy/surgery. If there is no such tumor assessment post randomization, the subject will be right censored on the date of randomization.
- Subjects who have not experienced an event (and are not otherwise censored) at the time of data cutoff will be right censored on the date of their last tumor assessment post randomization that is on or prior to the data cutoff. If there is no such tumor assessment post randomization, the subject will be right censored on the date of randomization.
- Subjects who miss 2 or more scheduled tumor assessments followed by an event will be right censored on the date of their most-recent tumor assessment prior to the missing assessments. If there is no such tumor assessment post randomization, the subject will be right censored on the date of randomization.

Hypothesis testing between the two treatment arms will be performed using the stratified log-rank test with a 2-sided 0.01 level of significance. The stratification factors will be the same as those used to stratify the randomization (see [Section 3.3](#)).

The median duration of PFS and the associated 95% and 99% CIs for each treatment arm will be estimated using the Kaplan-Meier method. The HR with 95% and 99% CIs will be estimated using a Cox regression model and will include the same stratification factors described above.

In the primary analysis of PFS, if the p-value for the stratified log-rank test is statistically significant and the HR ($\lambda_{\text{cabozantinib + atezolizumab}} / \lambda_{\text{sorafenib}}$) is < 1 , the null hypothesis of no difference between the two treatment arms in PFS will be rejected and it will be inferred that PFS is superior in the group receiving cabozantinib + atezolizumab compared with the group receiving sorafenib.

9.2.2.2. Overall Survival

The primary analysis of OS is event-driven and will be conducted after at least 368 deaths have been observed in the ITT population ([Section 9.1.1](#)) for the experimental and control arms.

Hypothesis testing between the two treatment arms will be performed using the stratified log-rank test with a 2-sided α level of significance (the α level will be defined per [Section 9.5](#)). The stratification factors will be the same as those used to stratify the randomization.

The median duration of OS and the associated 95% and 1- α % CI for each treatment arm will be estimated using the Kaplan-Meier method. The HR with 95% and 1- α % CIs will be estimated using a Cox regression model and will include the same stratification factors described above.

Details of interim analyses of OS are provided in [Section 9.8](#).

At any analysis of OS (interim or primary), if the p-value for the stratified log-rank test is statistically significant and the HR ($\lambda_{\text{cabozantinib + atezolizumab}} / \lambda_{\text{sorafenib}}$) is < 1 , the null hypothesis of no difference in OS between the two treatment arms will be rejected and it will be inferred that OS is superior in the group receiving cabozantinib + atezolizumab compared with the group receiving sorafenib.

9.2.2.3. Supportive Analyses

Supportive (sensitivity) analyses will be conducted using all PFS events and subjects in the ITT population ([Section 9.1.1](#)) for the experimental and control arms at the time of the primary PFS analysis in the PITT population (see [Section 9.1.1.1](#)). Additional sensitivity analyses of PFS will be defined in the SAP using alternative event definitions and censoring schemes to account for partial or completely missing assessments, address bias due to tumor assessment timing, and to evaluate the impact of potentially informative censoring. These analyses will be performed using the same statistical methods described for the primary analysis.

Exploratory analyses of the effect of baseline characteristics, stratification factors, and other variables on PFS and OS will be conducted using Cox regression models and subgroup analyses performed employing Kaplan-Meier methods.

9.3. Secondary Efficacy Endpoint

Formal hypothesis testing is planned for the secondary efficacy endpoint of PFS per BIRC for the single-agent cabozantinib arm vs the control arm (sorafenib).

9.3.1. Progression Free Survival (PFS) per BIRC between Single-Agent Cabozantinib and Control Arms

The analysis of PFS as a secondary endpoint is event-driven and will be conducted after at least 283 events have been observed in the ITT population (see [Section 9.1.1](#)) for the single-agent cabozantinib and control arms. It is designed to include progression events as determined by the BIRC per RECIST 1.1. General censoring rules as described in [Section 9.2.2.1](#) will be applied.

Hypothesis testing between the two treatment arms will be performed using the stratified log-rank test at the 2-sided α level (the α level will be defined per [Section 9.5](#)) in the ITT population, provided the null hypothesis for either PFS or OS is rejected in favor of the experimental arm (cabozantinib + atezolizumab) as described in [Section 9.5](#). The stratification factors will be the same as those used to stratify the randomization (see [Section 3.3](#)).

The median duration of PFS and the associated 95% and 99% CIs for each treatment arm will be estimated using the Kaplan-Meier method. The HR with 95% and 99% CIs will be estimated using a Cox regression model and will include the same stratification factors described above.

In the secondary analysis of PFS, if the p-value for the stratified log-rank test is statistically significant and the HR ($\lambda_{\text{cabozantinib}} / \lambda_{\text{sorafenib}}$) is < 1 , the null hypothesis of no difference between the two treatment arms in PFS will be rejected and it will be inferred that PFS is superior in the group receiving single-agent cabozantinib compared with the group receiving sorafenib.

One interim analysis of secondary PFS is planned at approximately 67% information fraction. Details are provided in [Section 9.8](#).

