The primary efficacy analyses in this study are the comparisons between the combination treatment and control arms for OS and PFS. These analyses will be performed for subjects enrolled in the global enrollment phase which will not include subjects enrolled in the Mainland China Extension Phase. Treatment with cabozantinib in combination with atezolizumab will be inferred to be superior to treatment with sorafenib if the null hypothesis of no difference between arms is rejected in favor of the experimental arm for either OS or PFS. Inflation of Type 1 error associated with multiple primary endpoints and the secondary efficacy endpoint of PFS between single-agent cabozantinib and sorafenib will be controlled by a closed testing procedure that employs a modified Bonferroni procedure, a gatekeeping technique, and the fallback method (see [Section 9.5](#)). The study-wise 2-sided alpha of 5% will be nominally divided between primary endpoints PFS (1%) and OS (4%), with the secondary PFS endpoint tested at the 1% level only if the primary PFS test is successful. If the null hypotheses are rejected for both the primary and secondary PFS endpoints, the 1% alpha for PFS will be reallocated to OS, allowing it to be tested at the 5% level.

Duration of OS is defined as time from randomization to death due to any cause. Duration of PFS is defined as time from randomization to the earlier of either PD per RECIST 1.1 as determined by the BIRC or death from any cause.

The primary analyses of OS and PFS will be event-driven and will be conducted independently after at least the number of events required for each analysis has been observed.

PFS and OS will be summarized descriptively using the Kaplan-Meier method. Inferential comparisons between treatment arms will use the stratified log-rank test. The HR will be estimated using a stratified Cox proportional hazards model. Stratification will be based on the stratification factors used for the randomization as recorded in the Interactive Response Technology (IRT) system.

The study is designed to provide adequate power for analyses of both primary endpoints of PFS and OS comparing the experimental arm with the control arm, and for the analysis of the secondary endpoint of PFS comparing the single-agent cabozantinib arm with the control arm. For the primary endpoints, a larger sample size is needed to provide reasonable power for OS

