Two interim analyses of OS are planned and will include all subjects in the ITT population available at the time of each analysis. These are planned at the 33% and 66% information fractions. The first interim analysis (IA1) will coincide with the primary analysis of PFS and will be performed only if the null hypothesis for primary PFS is rejected and is expected to occur at approximately the 33% information fraction. Should the timing of IA1 trend towards an information fraction much higher than expected (eg, due to faster-than-expected deaths or slower-than-expected PFS events), the plan for the interim analyses of OS may be modified (see [Section 9.8](#)). Inflation of Type 1 error associated with these interim analyses will be controlled using Lan-DeMets O’Brien-Fleming (LD-OF) alpha-spending functions based upon a 4% total alpha allocation for OS.

The secondary analysis of PFS for the single-agent cabozantinib arm vs the control (sorafenib arm) will be performed for subjects enrolled in the global enrollment phase which will not include subjects enrolled in the Mainland China Extension Phase. For this analysis, a total of 283 events among all 370 subjects (185 per arm) in the single-agent cabozantinib and control arms provides the study with 85% power for a 2-sided log-rank test with a 1% level of significance to detect a hypothesized true HR of 0.65. Assuming an exponential distribution for PFS, this

corresponds with a 53% increase in median PFS from 3.6 months to 5.5 months. The minimum observed effect that would result in statistical significance for PFS is an HR of 0.735, a 36% improvement in median from 3.6 to 4.9 months.

An interim analysis of secondary PFS is planned contemporaneously with the primary PFS analysis and will include all subjects in single-agent cabozantinib and control arms of the ITT population available at the time of the analysis. This is anticipated to be at 67% information fraction (to be performed only if the null hypothesis for PFS is rejected). Inflation of Type 1 error associated with these interim analyses will be controlled using Lan-DeMets O'Brien-Fleming (LD-OF) alpha-spending functions based upon a 1% total alpha allocation for secondary PFS.

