In recent years regulatory agencies have issued guidance for evaluating combination therapies requiring nonclinical and clinical evidence that supports the need for both components of the treatment regimen. In light of this guidance, direct discussions with regulatory agencies, and the limited amount of clinical data available for the administration of cabozantinib in the first-line HCC setting, a third treatment arm (approximately 185 subjects) will be enrolled in which subjects receive single-agent cabozantinib in order to determine its contribution to the overall safety and efficacy of the combination with atezolizumab in this patient population. Given the statistically significant improvement in OS and PFS demonstrated with single-agent cabozantinib in a previously treated HCC population and subsequent regulatory approval for cabozantinib to treat those patients, early observations of clinical activity in a previously untreated HCC population, and the demonstration of efficacy of other VEGFR-TKIs (eg, sorafenib, lenvatinib) in a previously untreated HCC population, exploration of cabozantinib (at the recommended single-agent dose of 60 mg) in a previously untreated HCC population is justified. A formal planned analysis of PFS for the single-agent cabozantinib arm vs the control arm (sorafenib) as a secondary endpoint will evaluate the relative efficacy of those two agents and will provide the basis for establishing the contribution of cabozantinib to combination therapy administered in the experimental arm.

In order to evaluate the full clinical benefits of the combination therapy of cabozantinib with atezolizumab, the current Phase 3 study includes analyses of health-related quality of life (HRQOL), healthcare resource utilization, pharmacokinetics (PK), and biomarkers.

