9.5. Control of Type I Error

Inflation of Type 1 error associated with testing of multiple primary endpoints and a secondary efficacy endpoint (PFS between single-agent cabozantinib and control) will be controlled by a modified Bonferroni procedure, a gatekeeping technique, and the fallback method (FDA 2017). Initially, the study-wise 2-sided alpha of 5% will be unequally allocated between primary endpoints PFS (1%) and OS (4%). The secondary PFS endpoint will be tested at the 1% level only if the primary PFS test is successful. If the null hypotheses are rejected for both the primary and secondary PFS endpoints, the 1% alpha for PFS will be reallocated to OS, allowing it to be tested at the 5% level.

Two interim analyses of OS are planned at the 33% and 66% information fractions (the first interim will coincide with the primary analysis of PFS and will be performed only if the null hypothesis for PFS is rejected and is expected to occur at approximately the 33% information fraction). One interim analysis is planned for secondary PFS endpoint contemporaneous with the primary PFS analysis with anticipated information fraction of 67%. Type 1 error associated with interim analyses will be controlled using Lan-DeMets O'Brien-Fleming (LD-OF) alpha-spending functions based upon a 4% total alpha allocation for OS and 1% for secondary PFS.

The testing and alpha reallocation are elucidated below.

First, test primary PFS at the 1% level. Then:

1. If primary PFS is significant:
 - a. Re-allocate its 1% alpha to secondary PFS per the fallback method.
 - b. Conduct interim analysis of OS at 33% per LD-OF with 4% total alpha
 - c. Conduct interim analysis of secondary PFS endpoint at 67% per LD-OF with 1% alpha.
 - i. If interim analysis of secondary PFS is significant:
 - Re-allocate its 1% alpha to OS
 - Conduct interim analysis of OS at 66% per LD-OF with 5% alpha
 - No further inferential testing of secondary PFS will be performed.

- ii. If interim analysis of secondary PFS is not significant:
 - The final analysis of secondary PFS will be conducted at an alpha of 0.0096.
 - The alpha of subsequent OS analyses will be dependent on the timing and result of the final secondary PFS analysis.

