 - The second interim analysis and the final for OS will be conducted per LD-OF with 4% alpha, if the second interim analysis occurs prior to the final analysis for secondary PFS, or, if it occurs after the final secondary PFS analysis where the final secondary PFS fails to reject its null hypothesis.
 - The subsequent OS analyses will be conducted per LD-OF with 4.96% alpha if it occurs after the rejection of the null hypothesis for secondary PFS.
- d. Conduct interim and final analyses of OS with appropriate alpha as determined above

2. If primary PFS is not significant:

- a. Secondary PFS analysis cannot be conducted
- b. Conduct interim and final analyses of OS per LD-OF with 4% total alpha
 - i. If OS is not significant at final analysis, procedure ends

All other statistical evaluations of efficacy will be considered exploratory.

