^d The interim analysis at 66% information fraction will be conducted at 4% alpha level if it occurs prior to the secondary PFS analysis. It will be conducted at 4.96% alpha level if it happens after the null hypothesis for secondary PFS is rejected at the time of final analysis. It will be conducted at 5% alpha level only if the null hypothesis for secondary PFS is rejected at the interim analysis.

Rejection of the null hypotheses for OS at the first interim analysis at about 33% information is not expected: it is designed primarily as an administrative analysis, expected to coincide with the primary analysis of PFS, and will be performed only if the null hypothesis for PFS is rejected.

Should the timing of the first interim analysis (IA1) of OS trend towards an information fraction much higher than expected (eg, due to faster-than-expected deaths or slower-than-expected PFS events), the interim analyses of OS will be conducted as follows:

OS IA1 IF	Proceed as	Rationale
< 50%	perform IA1 and IA2 as planned above	similar conditions to original plan
50 to < 66%	
 perform IA1 at time of primary PFS, irrespective of whether PFS null hypothesis is rejected or not Conduct IA2 at 80% IF (instead of 66%) 	
 Higher than expected information for OS negates administrative nature of the analysis. Preserves two interim analyses as planned with reasonable intervals between them
≥ 66%	perform a single interim analysis at 66% IF, irrespective of timing or results of primary PFS analysis.	Information fraction meets or exceeds that of planned analysis at 66%

IA1, first interim analysis; IA2, second interim analysis; IF, information fraction; OS, overall survival

An interim analysis of secondary PFS is planned contemporaneously with the primary PFS analysis and will be conducted only if the null hypothesis for primary PFS is rejected. It is anticipated to be at approximately 67% information fraction based on a total alpha of 1%. At this fraction, the critical p-value is 0.0096, and the maximum HR to reject the null hypothesis is 0.626.

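### Protocol 9.3.1 opens the formal single-agent PFS test on success in either PFS or OS; Section 9.5, which it cites, opens it on primary PFS only

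*Protocol*

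**What the plan says.** Protocol 9.3.1 defines the only secondary efficacy endpoint, BIRC-assessed PFS for single-agent cabozantinib against sorafenib. It calls for a stratified log-rank test among ITT subjects, on this condition: "provided the null hypothesis for either PFS or OS is rejected in favor of the experimental arm (cabozantinib + atezolizumab) as described in"; the reference is to Section 9.5. It sets no significance level of its own: "the α level will be defined per" Section 9.5.

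The gate is stated elsewhere as follows:

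- **Protocol 9.5, opening paragraph:** "The secondary PFS endpoint will be tested at the 1% level only if the primary PFS test is successful". Step 1a adds that this 1% is the alpha released by primary PFS.
- **Protocol 9.5, branch 2 (primary PFS not significant):** "Secondary PFS analysis cannot be conducted". The branch then tests OS at 4% and stops.
- **Protocol synopsis, Statistical Methods:** "with the secondary PFS endpoint tested at the 1% level only if the primary PFS test is successful".
- **SAP 7.2:** the same sentence as the opening paragraph of Protocol 9.5.

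For the interim look at this endpoint only, the synopsis says "to be performed only if the null hypothesis for PFS is rejected". Protocol 9.8 says the look "will be conducted only if the null hypothesis for primary PFS is rejected", and SAP 7.3 repeats that wording. SAP 7.4.1, the SAP counterpart of 9.3.1, states no gate.

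**The concern.** Section 9.3.1 attributes to 9.5 a rule that 9.5 does not contain and, in one branch, expressly forbids. This is more than loose wording. A gate that opens on either endpoint includes the case where primary PFS fails and OS succeeds, and that is the case in which 9.5 says the analysis is not to be done.

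The endpoint carries weight. Protocol 1.5.2 says this comparison "will provide the basis for establishing the contribution of cabozantinib to combination therapy administered in the experimental arm". If primary PFS failed and OS succeeded, a reader working from 9.3.1 would expect a formal test and, if it were significant, a superiority conclusion. A reader working from 9.5 would expect neither. A pre-specified confirmatory test should have one gate.

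**Working it through.** **1. The plan's own figures reproduce.** The Schoenfeld approximation gives power = Φ(|ln HR| × √(d·p·(1−p)) − z), where d is the number of events, p the allocation fraction and z the two-sided critical value. Inputs are from Protocol 9.7.

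| Test | Inputs | Calculation | Power | Stated |
|---|---|---|---|---|
| Secondary PFS | 283 events, 1:1, HR 0.65, α 0.01 | Φ(0.4308 × √70.75 − 2.576) | 85.3% | 85% |
| Primary PFS | 257 events, 2:1, HR 0.60, α 0.01 | Φ(0.5108 × √57.11 − 2.576) | 90.1% | 90% |
| OS | 368 events, 2:1, HR 0.69, α 0.04 | Φ(0.3711 × √81.78 − 2.054) | 90.4% | 90% |

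Solving the first row for events at 85% power gives 282 against the stated 283. The alpha split is 1% + 4% = 5%.

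**2. The two gates side by side.**

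| Primary PFS | OS | Secondary PFS under 9.3.1 | Secondary PFS under 9.5 |
|---|---|---|---|
| rejected | rejected | tested | tested at 1% |
| rejected | not rejected | tested | tested at 1% |
| not rejected | rejected | **tested** | **not tested, no alpha** |
| not rejected | not rejected | not tested | not tested |

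Only the third row differs. Section 9.5 has no step that passes alpha from OS to secondary PFS.

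**3. How often the third row arises at the design effects.** Under independence it is (1 − 0.9005) × 0.9035 = 0.0899, or 9.0%. The documents give no correlation between the primary PFS and OS statistics, so I took a range and used the bivariate normal distribution:

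| Assumed correlation | 0 | 0.3 | 0.5 | 0.7 | 0.9 |
|---|---|---|---|---|---|
| P(primary PFS fails, OS succeeds) | 9.0% | 7.9% | 6.8% | 5.4% | 3.2% |

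This is the chance of reaching the disputed branch, not the chance of a wrong test.

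If primary PFS has no effect and OS has its design HR of 0.69, the 9.5 gate opens about 1% of the time. The 9.3.1 gate would open 1 − 0.99 × (1 − 0.9035) = 0.904, about 90% of the time (independence, single look).

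**4. Whether error control is at risk.** The case in which the two gates separate most is a real OS effect with both PFS nulls true.

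- *Gate in 9.5:* an error requires rejecting primary PFS first, so family-wise error is 1.0%.
- *Gate in 9.3.1, with the test run at 1%:* under independence, 0.01 + 0.99 × 0.9035 × 0.01 = 0.0189, or 1.9%. Simulation with 8 million draws per setting gave 1.7% to 1.9%. It took the correlation of primary PFS with OS from 0 to 0.7, and of primary with secondary PFS as 0 or 0.5. With an OS effect so large that OS is always rejected, the figure is about 2.0%.

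In a separate simulation of the other combinations of true and false nulls, family-wise error under either gate did not exceed 5% beyond simulation error.

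**The case against.** The strongest reply is that the plan already resolves the conflict. Section 9.3.1 supplies no alpha and sends the reader to 9.5 for both the level and the gate. Section 9.5 then blocks the test when primary PFS fails, and both 9.5 and SAP 7.2 class every other efficacy evaluation as exploratory. The SAP, from which the analysis will be programmed, never contains the either-endpoint gate. No design figure changes, and family-wise error would stay within 5% even if the looser gate were applied at 1%.

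All of that stands, and it is why the point should be rated no higher than a correction worth making. It does not make the sentence right: the cross-reference leads to text that contradicts the sentence citing it.

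The branch probabilities also deserve the criticism that independence is not a realistic base case. Deaths count as PFS events, and the PFS population is a subset of the OS population. The lower figures are therefore more plausible than 9.0%, and all of them treat OS as a single look although two interim analyses are planned.

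**Conclusion.** The inconsistency is real, and 9.3.1 is wrong as written. No other section of the protocol or SAP supports a gate that opens on OS alone.

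The practical size is small. Section 9.5 governs, the disputed branch has a probability of 3.2% to 9.0% at the design effects, and there is no effect on events, power or the 5% study-wise alpha. Those probabilities rest on the Schoenfeld approximation, single-look tests and assumed correlations. The point does not claim type I error inflation and should not be read that way. It should be fixed because the section that defines a formally tested endpoint states the wrong decision rule for it.

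**What to change.** In Protocol 9.3.1, replace the condition that either the PFS or the OS null hypothesis is rejected with the condition that the primary PFS null hypothesis is rejected. Keep the reference to Section 9.5. This matches the rule already in the synopsis, Protocol 9.5 and SAP 7.2.

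The cost is one phrase: the 283 events, 85% power and 1% level for this test are unchanged. Section 9.5 and the SAP's testing rule need no edit. As an optional tidy-up, SAP 7.2 labels the procedure parallel gatekeeping, which sits poorly with a gate that depends on PFS alone; the label could be aligned with Protocol 9.5 at the next SAP revision.
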